2. Morbidity and mortality: morbidity and mortality will be evaluated using the prospective database of the Bariatric Surgery Unit and the electronic medical record of each patient. All perioperative aspects related to the surgery will be reviewed. Complications will be recorded according to the Clavien-Dindo classification.
3. Metabolic comorbidities: Comorbidities related to metabolic syndrome and morbid obesity will be recorded to study their evolution up to 5 years after the intervention: DM2, hypertension, DL and OSAS.
4. Medical team coordination and satisfaction using the APP vs. standard protocol will be evaluated during multidisciplinary committee.
5. Patients weight loss 3 months after surgery will be evaluated using the prospective database of the Bariatric Surgery Unit and the electronic medical record of each patient.
6. Nutritional and metabolic deficiencies: The analytical studies performed each year on these patients will be evaluated to detect possible deficiencies: protein, iron, phosphocalcic, fat-soluble vitamins and trace elements.

STUDY DURATION:

The study is expected to begin in October 2022

Patient recruitment period is expected from October 2022 to March 2024.

Preoperative follow-up will be completed the day of surgery.

Mid-term follow-up (2 years) will be completed in March 2026.

Long-term follow-up (5 years) will be completed in March 2029.

SAMPLE SIZE:

The sample size was calculated in 142 patients divided into two groups of 71 patients each. It was calculated by comparing a hypothetical reduction of ≥ 5 kg in 55% of patients in the C4T group vs in 39% of patients in the control group [27] with a possible loss of 16% of patients, a confidence level of 95%, and statistical power of 80%.

STATISTICAL ANALYSIS:

Continuous variables will be expressed as mean \pm standard deviation or median (interquartile range) as appropriate. Differences between both techniques will be evaluated using a parametric test (χ^2 for categoric variables and t test for continuous variables). We'll use the IBM-SPSS Statistics Version 20 computer software to analyse all the statistics. A p value < 0.05 will be considered statistically significant.

PERSONAL DATA PROTECTION / CONFIDENTIALITY / ETHICAL ASPECTS:

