Appendix 3: Questionnaire to assess patients' satisfaction:

PATIENT SATISFACTION QUESTIONNAIRE – VAMOS PROJECT

	Scarce	Poor	Good	Very good	Excellent
1. Kindness/Courtesy of the medical team.....					
2. Explanations of the medical team about your pathology.....					
3. Interest that the team has shown in clearing up your doubts and concerns.....					
4. Willingness of the medical team to include you in treatment decisions					
5. Information provided by the team on the type of medication.....					
6. Instructions provided by the medical team on follow-up.....					
7. Comprehensibility of the language of the information received.....					
8. Time that the medical team has dedicated to you.....					
9. Your confidence in this medical team.....					
10. Probability that you recommend this medical team to other patients.....	

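### Chi-square is the only test named for categorical outcomes, though satisfaction items and Clavien-Dindo grades are ordered; tested as multi-level tables, these secondary comparisons would lose power

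*Combined protocol and SAP*

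**What the plan says.** The statistical analysis section of the combined protocol and SAP is one short paragraph. It describes its tests as parametric and lists chi-square "for categoric variables and t test for continuous variables". The threshold is "A p value < 0.05 will be considered statistically significant". Continuous variables may be summarised by mean and standard deviation "or median (interquartile range) as appropriate", but no test is paired with the median. No rank, trend or ordinal method appears anywhere.

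Two of the secondary goals rest on data collected on ordered scales:

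- **Complications.** The secondary criteria say "Complications will be recorded according to the Clavien-Dindo classification". The comparisons listed under study design are of morbidity and mortality at 30 and 90 days.
- **Patient satisfaction.** Appendix 3 has ten items, for example "Explanations of the medical team about your pathology", each answered on five levels from Scarce to Excellent.

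The documents do not say whether complications are compared by grade or as present/absent. Nor do they say whether satisfaction is compared item by item or as a total score.

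**The concern.** A Clavien-Dindo grade and a five-level answer are both categorical, so on a literal reading chi-square is the test the plan assigns to them. Pearson's chi-square treats the levels as unordered. It spreads its sensitivity over 4 degrees of freedom for a five-level item, or 5 for six complication levels (none, I to V). A shift towards better or worse levels can be tested on 1. Where most patients have no complication, the higher grades also have very small expected counts, and the test becomes conservative.

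At stake are two secondary comparisons that could miss a difference the same data would show with another standard test. Because the coding is not fixed, it could also be chosen after the data are seen. Separately, a score judged skewed enough to be reported as a median has no matching comparison in the plan.

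**Working it through.** **Inputs from the documents.** The plan states: "The sample size was calculated in 142 patients divided into two groups of 71 patients each". It allows for 16% loss, so 71 × 0.84 = 59.6, about 60 evaluable per arm. The significance level is 0.05; sidedness is not stated, and two-sided is assumed. The documents give no power figure for any ordered outcome, so there is none to reproduce. How the total of 142 was derived is a separate question; it serves here only as the sample size.

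**Inputs assumed, because the documents give none.**

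- Clavien-Dindo pattern A (none, I to V): 0.78 / 0.08 / 0.08 / 0.04 / 0.015 / 0.005, that is 22% with any complication; odds ratio 2.
- Clavien-Dindo pattern B: 0.85 / 0.06 / 0.05 / 0.03 / 0.008 / 0.002, that is 15%; odds ratio 2.5.
- Satisfaction item: 0.02 / 0.08 / 0.30 / 0.35 / 0.25; odds ratio 2.
- The other arm follows by a proportional-odds shift.

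**Step 1: sparseness.** Expected count per arm under no difference = 71 × probability.

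- Pattern A, grades I to V: 5.7, 5.7, 2.8, 1.1, 0.4. Three of the five are below 5.
- Pattern B, grades I to V: 4.3, 3.6, 2.1, 0.6, 0.1. All five are below 5.

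**Step 2: cost of the extra degrees of freedom.** At the noncentrality that gives 80% power on 1 df, the noncentral chi-square gives 60% on 4 df and 56% on 5 df. Starting from 50%, it gives 31% and 28%. This approximation leaves out the added effect of sparse cells.

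**Step 3: simulation.** Pearson chi-square on the non-empty levels was compared with the tie-corrected Mann-Whitney test and with the plan's own tests on simpler codings. Ranges cover repeated runs of 6,000 to 20,000 simulated trials.

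| Setting | Per arm | Chi-square, all levels | Mann-Whitney | Plan's test on simpler coding |
|---|---|---|---|---|
| Grades, A, OR 2 | 71 | 14–15% | 33–34% | 33–34% (any complication, 2×2) |
| Grades, B, OR 2.5 | 71 | 14–16% | 35–37% | 36–38% (2×2) |
| Satisfaction item, OR 2 | 71 | 39–40% | 61–63% | 60–62% (t test on scored item) |
| Grades, A, OR 2 | 60 | 12% | 28–29% | 28% (2×2) |
| Grades, B, OR 2.5 | 60 | 11–12% | 29–32% | 31% (2×2) |
| Satisfaction item, OR 2 | 60 | 32–33% | about 54% | about 53% (t test) |

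With no true difference, the graded chi-square rejected in about 3% of trials and the rank test in about 5%.

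**Step 4: check of the 2×2 column by formula.** Power = Φ{[(p1 − p2)√n − 1.96√(2p̄(1 − p̄))] / √(p1(1 − p1) + p2(1 − p2))}, with n = 71.

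- Pattern A: odds 0.22/0.78 = 0.282; halved, 0.141; p2 = 0.124; power 33%.
- Pattern B: odds 0.15/0.85 = 0.176; divided by 2.5, 0.0706; p2 = 0.066; power 36%.

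Both agree with the simulation.

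**Step 5: sensitivity.** Other assumed shapes were tried at 60 and 71 per arm. For five-level items, the relative loss from chi-square against the rank test was 42–48% at odds ratio 1.5, 34–42% at 2, 22–33% at 2.5 and 12–23% at 3. For grades, with complication rates of 10–30% and odds ratios of 1.5 to 3, it was 36–78%. The true size of the graded test was then 1.7–3.6%, and at least one expected count fell below 5 in 98–100% of trials.

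**The case against.** A reader might infer that the plan prescribes chi-square for Clavien-Dindo grades and single satisfaction items, and so gives up a third to more than half of the power. The documents do not support that, for three reasons.

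1. **The tabulation is not stated.** Clavien-Dindo is mentioned once, as a recording rule. The listed comparison of morbidity and mortality reads naturally as yes/no, and patient satisfaction is listed as a single level, which could be a score from the ten items.
2. **On those readings the plan's two tests are adequate.** In Step 3, the 2×2 chi-square and the t test come within about two percentage points of Mann-Whitney, and both hold their size at 4–5%.
3. **The percentage is not a property of this trial.** It depends on assumed distributions and effects, and on a proportional-odds shift, which suits a rank test. A loss above one half arises only for sparse grades; for items it falls to 12–23% at an odds ratio of 3.

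These are also secondary outcomes. For complications, even the better tests reach less than 40% power in the main settings.

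All of this stands as a limit on size. It does not remove the point. The plan writes down neither the yes/no coding nor the score, and its one rule for a categorical variable is chi-square. The missing test for medians needs no assumption at all.

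**Conclusion.** The point holds in conditional form. The plan's only rule for categorical outcomes ignores order, although it collects ordered outcomes and foresees medians without a matching test.

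If the ordered outcomes are tested as multi-level tables at 71 per arm under the assumptions above, power is:

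- for a satisfaction item, about 40% against 62%, a relative loss of 1 − 40/62 = 35%;
- for Clavien-Dindo grades, about 15% against 33–37%, a relative loss of 1 − 15/33 = 55% to 1 − 15/37 = 59%, with true size about 3%.

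If complications are tested as yes/no and satisfaction as a score, the loss is close to nil. The error is one of missed effects: false positives are not inflated. The primary comparison, a continuous percentage of preoperative weight loss, is not touched. The change should be made because it is standard and nearly free, but it does not threaten the trial's main conclusion.

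**What to change.** In the statistical analysis section:

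- Name Mann-Whitney or proportional-odds regression for ordered outcomes: the satisfaction items, and the worst Clavien-Dindo grade per patient with 'none' as the lowest level.
- Use Mann-Whitney wherever a median with interquartile range is reported.
- For complications, a prespecified any-complication yes/no comparison by chi-square is an equally good alternative. State which of the two will be used.
- State whether satisfaction is compared by item or by total score.
- Keep chi-square for yes/no outcomes.

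The cost is one or two sentences. It needs no extra data, patients or unusual methods. It should be settled before outcomes are examined by group.

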All patients will receive the standard preoperative protocol that consist in optimization of associated complications with an active management of obesity-related comorbidities, optimization of preoperative weight loss through a hypocaloric diet carried out during the 10-15 days prior to surgery and an informative and educational group session prior to surgery (EDUBAR). The C4T APP will be provided four months before surgery to all the patients randomized in the APP group. All the contents in the APP have been properly selected and modified by the multidisciplinary team (endocrinologist, pneumologist, anaesthesiologist, psychiatrist, nutritionist, nursery). Specifically, the APP contents include informative articles covering the nutritional, behavioral, and surgical fields, exercises, interactive charts, instructional videos, surgical animations, checklists, and frequently asked questions. The format of the APP will lead the patient through a virtual journey in the world of bariatric surgery, allowing to understand all the basic information about the preoperative period, the surgery and hospitalization and the postoperative follow-up. The use of the APP will influence preoperative weight loss through all the information provided, designed in an intuitive way so that the patient progresses in their level of knowledge and can assess through a checklist if they are doing the correct training. It will allow patients to set specific goals and assess their scope. Making patients aware of the importance of preoperative weight loss through training will be the key to obtaining correct adherence to the program and satisfactory preoperative weight loss. No patient data will be saved on the APP.

To assess the impact of the APP, in addition to standard protocol, in the pre- and postoperative period, we will compare:

- preoperative total weight loss percentage
- level of patient information
- level of patient satisfaction
- level of medical team satisfaction
- 30th and 90th days postoperative morbidity and mortality
- percentage of weight loss 3 months after surgery

CHRONOGRAM:

OBSERVATION PERIOD

Recruitment period of the study is expected to be 18 months, with additional 6 months to perform surgeries and follow-up. All information's will be obtained using the application flow of data alongside with presential meeting with surgeons, endocrinologists, nutritionists.

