S. All the contents in the APP have been properly selected and modified by the multidisciplinary team. The day of surgery all the data about weight loss, patient and medical team satisfaction will be collected. Then, patients will be followed in observation of our standard postoperative protocol to assess the 30th and 90th postoperative morbidity and mortality alongside with weight loss evolution. The PhD student has been directly involved in the APP design and contents creation. He will perform the preoperative presential meeting to provide and explain the APP functioning to the patients in the APP group. Furthermore, he will collect the data on the day of surgery, during surgery and will be directly involved in postoperative follow-up of all patients.

STUDY POPULATION:

Inclusion criteria:

- Patients older than 18 and younger than 65 years who meet criteria to undergo bariatric surgery
- BMI between 35 and 50 kg/m² and indication of one-time surgery
- Signing the informed consent of the study
- Patient suitable for laparoscopic surgery
- Patient who demonstrates accessibility to a smartphone and basic digital competence (Appendix 1).

Exclusion criteria:

- Previous bariatric surgery
- Two-step surgery
- Patient without resources to access the use of a Smartphone or without basic digital competence
- Contraindication for surgery
- Other surgical procedures associated with the same intervention

Retirement criteria:

- None

EXPERIMENTAL TREATMENT: Use of a mobile application to accompany and empower patients in the preoperative period.

EVALUATION CRITERIA:

Main criteria (for the main goal): Preoperative percentage of excess weight lost (%EWL), considering ideal BMI = 25, will be recorded.

Following the follow-up protocol in General Surgery Outpatient Consultations, patients' weight will be measured 4 months before surgery and on the same day of surgery; then at 3, 6 and 12 months, and then every year up to 5 years of follow-up to calculate BMI and percentage of overweight lost, percentage of BMI lost, total weight and BMI lost.

Secondary criteria (for secondary goals):

1. Patients' information and satisfaction using the APP vs. standard protocol will be evaluated using approved questionnaire (appendix 2, appendix 3);

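### Preoperative %EWL is to be compared by an unadjusted t test although baseline BMI, part of its definition, is known for every patient; prespecifying BMI as a covariate is a small refinement that needs no new data

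*Combined protocol and SAP*

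**What the plan says.** All references are to section 1 (Resume) of the combined protocol and SAP.

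- **Evaluation Criteria, main criterion:** "Preoperative percentage of excess weight lost (%EWL), considering ideal BMI = 25, will be recorded".
- **Statistical Analysis:** χ² for "categoric variables and t test for continuous variables", judged at p < 0.05. This general sentence is the only analysis rule that reaches %EWL. No covariate, adjusted model or stratification factor appears anywhere.
- **Study Population:** eligibility requires "BMI between 35 and 50" kg/m², so BMI is established for every patient at entry.
- **Evaluation Criteria, weighing schedule:** "patients' weight will be measured 4 months before surgery and on the same day of surgery".
- **Study Design:** "The C4T APP will be provided four months before surgery" to the app arm. This section also lists "preoperative total weight loss percentage" among the comparisons.
- **Sample Size:** 71 patients per arm with 16% loss, based on a loss of at least 5 kg "in 55% of patients in the C4T group vs in 39% of patients in the control group".

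**The concern.** With a fixed ideal BMI, %EWL is not a pure measure of how much a patient lost. The same proportional loss scores higher in a lighter patient, because the excess weight in the denominator is smaller. Baseline BMI should therefore predict the outcome whenever mean loss is above zero, unless proportional loss happens to rise with BMI by enough to cancel the effect.

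An unadjusted t test leaves the BMI-related spread in the error term. It also leaves in the estimate any arm difference that arises only because one arm started with a lower BMI by chance. Averaged over randomisations there is no bias. In the one trial that is run, however, an imbalance may appear, and an adjustment introduced afterwards would look data-driven.

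**Working it through.** **Plan's own figure.** There is none on this point. The 142 patients were derived for a responder proportion and are used here only as the number available.

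**Algebra.** Height is constant, so %EWL = 100 × (BMI₀ − BMI₁)/(BMI₀ − 25) and percentage total weight loss is %TWL = 100 × (BMI₀ − BMI₁)/BMI₀. Hence %EWL = %TWL × BMI₀/(BMI₀ − 25).

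| Baseline BMI | Multiplier | %EWL for a 5% weight loss |
|---|---|---|
| 35 | 35/10 = 3.5 | 17.5 |
| 50 | 50/25 = 2.0 | 10 |

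**Inputs from the documents.** BMI 35–50; evaluable per arm 71 × 0.84 = 59.6, taken as 60; 39% and 55% losing at least 5 kg.

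**Assumptions, since the documents give no SD, mean loss, mean weight or correlation.** BMI normal with mean 43 and SD 4, limited to 35–50 (resulting mean 42.9, SD 3.40); SD of %TWL s = 3 or 4 points; mean weight W = 110–125 kg.

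**Mean loss implied by the plan.** On a normal scale, a proportion p losing at least 5 kg implies a mean of 100 × 5/W + s × z(p). With z(0.39) = −0.279 and z(0.55) = 0.126, the two-arm average of z is −0.077.

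- W = 110: 4.55 − 0.077s = 4.31% (s = 3) or 4.24% (s = 4)
- W = 120: 4.17 − 0.077s = 3.94% or 3.86%
- W = 125: 4.00 − 0.077s = 3.77% or 3.69%

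The range is about 3.7–4.3%; 4% is used below.

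**Variance explained and gain in precision.** R² comes from simulation. The theoretical CI-width ratio is √(1 − R²). The net ratio comes from simulated trials of 60 per arm and pays for the extra coefficient.

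| Case | s | R² | √(1 − R²) | Net ratio |
|---|---|---|---|---|
| % loss unrelated to BMI | 3 | 0.0247 | 0.988 | 0.991 |
| % loss unrelated to BMI | 4 | 0.0142 | 0.993 | 0.997 |
| kg lost unrelated to BMI | 3 | 0.0652 | 0.967 | 0.971 |
| kg lost unrelated to BMI | 4 | 0.0381 | 0.981 | 0.985 |

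The net narrowing is 0.3–0.9% in the first case and 1.5–2.9% in the second. Type I error was about 5% with either analysis. Over mean losses of 3.7–4.3%, R² is 0.012–0.029 and 0.033–0.075 respectively.

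**Chance imbalance.** The SE of the between-arm BMI difference is 3.40 × √(2/60) = 0.62 kg/m², and a difference at least this large occurs in about one trial in three.

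- % loss unrelated to BMI: slope −0.35 points per kg/m², shift 0.35 × 0.62 = 0.22 points. The SE of the contrast is 1.37 (s = 3) or 1.82 (s = 4), so the shift is 0.16 or 0.12 SE.
- kg lost unrelated to BMI: slope −0.60, shift 0.60 × 0.62 = 0.37 points. The SE is 1.45 or 1.90, so the shift is 0.26 or 0.19 SE.

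**Wider assumptions.** Other plausible inputs (mean loss 5–8 kg with SD 3–6 kg, or 4.5–7% with SD 3–4.5 points) give R² of 0.015–0.145, which would lift a t test with 80% power to about 81–86%. The top of that range needs BMI spread evenly over 35–50, together with either a mean loss of 8 kg or an SD of only 3 kg. It should not be taken as the expected gain.

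**The case against.** The t test is valid, nothing in the plan is contradicted, and the gain is close to nil. If 55% versus 39% is read as a standardised difference of 0.405, adjustment adds only about 0.1–2.5 percentage points of power. This is true, and it is why the point is a suggestion only.

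The 3.5 and 2.0 multipliers are the extremes of the entry range. Under the assumed BMI distribution, 90% of patients have multipliers between 2.07 and 3.07. That is also correct: the extremes show the mechanism, and the R² values show its size.

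A linear BMI term removes only part of the spread due to the multiplier. Because %EWL is a product, the multiplier also scales the residual, and when percentage loss is unrelated to BMI roughly half to 60% of that variance is removed. This stands as a limit on the remedy, but the net ratios above already reflect it.

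Finally, the point depends on an outcome that is not settled. If total weight loss percentage is the outcome, BMI explains only 0–1.1% of its variance; if the 5 kg responder is the outcome and is tested by χ², the point does not apply. That condition stands and is carried into the fix.

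**Conclusion.** The point holds as a minor, optional improvement. The main criterion contains baseline BMI, that BMI is known for everyone, and the plan does not use it. Under the stated assumptions the net narrowing of the confidence interval is 0.3–2.9%, and a typical chance imbalance of 0.62 kg/m² moves the contrast by 0.12–0.26 of its standard error. The size rests on assumed BMI, weight and SD values. The direction follows from the definition of %EWL, unless proportional loss rises with BMI enough to offset it. Adjustment repairs neither the sample size nor the inconsistent outcome definitions, which are separate and larger matters.

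**What to change.** Once the outcome scale is settled, and if %EWL stands:

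1. Prespecify ANCOVA of preoperative %EWL on treatment arm and baseline BMI, using the value from four months before surgery. Report the adjusted mean difference with its 95% CI.
2. Keep the unadjusted t test as a sensitivity analysis.
3. State that the baseline weight is taken before the app is provided. The plan places both at four months before surgery and does not give the order.

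If total weight loss percentage becomes the main outcome, the same model applies with a smaller gain. If the 5 kg responder is chosen and tested by χ², no change is needed on this point.

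The cost is two sentences in the analysis section and one on timing. No new data are required, one residual degree of freedom is spent, and the named software fits the model.

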	SCARCE or NONE. Most of the time I have to ask someone more expert than me for help.
	SHORT. I defend myself, but with difficulty.
	NORMAL. I get to do the things I need to.
	ADVANCED. I consider that I know how to do more things than the rest of the people.
	EXPERT LEVEL. I have technical training. I am able to create content, program, etc.

